## 1.2. Study Design

Overview of Study Design and Key Features	

* Progression (a) on, or within 60 days of completion of the last therapy or (b) must be non-responsive while on last treatment, where non-responsive is defined as not achieving at least Minimal Response (MR) after 2 complete treatment cycles
 
** Stratification based on International Staging System (ISS), number of prior lines of therapy and prior usage of anti-CD38 antibody treatment
 
*** Until progressive disease (PD), death, unacceptable toxicity, withdrawal of consent, lost to follow-up or end of study, whichever comes first
	

Design Features
	
 
• This study is a Phase III, open-label, randomized, multicenter study evaluating the efficacy and safety of single agent belantamab mafodotin compared to pom/dex in participants with RRMM.
 
• The study will include a screening period, study treatment period, and follow-up.                         
 
○ During Screening, participants will be evaluated for study eligibility per protocol as defined in the Inclusion/Exclusion criteria (see Section 6 of Protocol Amendment 3). Eligible participants must have been previously treated with at least two prior lines of therapy, including at least 2 consecutive cycles of lenalidomide and a proteasome inhibitor (PI), (given separately or in combination) and must have documented progression (a) on, or within 60 days of completion of the last therapy or (b) must be non-responsive while on last treatment, where non-responsive is defined as not achieving at least Minimal Response (MR) after 2 complete treatment cycles. In such cases lack of achieving of MR must be determined no earlier than at least 4 weeks after the last treatment.
 
○ Following Screening, approximately 320 participants will be centrally randomized in a 2:1 ratio to either Arm 1 (single agent belantamab mafodotin) or Arm 2 (pom/dex), as described in Section 1.1 of Protocol Amendment 3. Participants will be stratified based on the following: previous treatment with anti-CD38 (Y/N), with a 40% global enrolment cap for participants with prior anti-CD38 treatment, stage (International Staging System [ISS]) (I/II or III), with a 55% global enrolment cap for participants with ≤3 prior lines. No cross-over will be allowed until final OS analysis.
 
○ During the Study Treatment Period, safety and disease assessments will be performed regularly according to the schedule of activities (Section 2 of Protocol Amendment 3) for each arm. Participants in both arms will be treated until PD, death, unacceptable toxicity, withdrawal of consent, loss to
 
 
 

Overview of Study Design and Key Features	
	
follow-up or end of study, whichever comes first. End of study is defined in Section 5.4 of Protocol Amendment 3. Dose interruptions or reductions may be required following potential drug-associated toxicities.
 
CCI [REDACTED]
 
 
○ For participants who discontinue study treatment for reasons other than PD, disease evaluations will continue to be performed every 3 weeks (<math>\pm 3</math> days) until confirmed (documented) PD, death, start of a new anticancer treatment, withdrawal of consent, or end of the study, whichever occurs first. In case of PD, participants will be followed to ascertain survival status CCI [REDACTED] every 12 weeks (<math>\pm 14</math> days) until withdrawal of consent, lost to follow-up, death or the end of the study.
 
● The final PFS analysis (primary analysis) will be conducted at the time of observing approximately 151 PFS events.
 
● A participant is considered to have completed the study if they are followed until death or end of study.
 
● End of study is defined as when the planned 250 deaths for final OS analysis have occurred, or when all participants have died or are lost to follow up or have withdrawn consent, whichever occurs first. At the first OS interim analysis (~40% OS information fraction), the study will not be stopped regardless of the results. GSK will continue to collect the OS data to conduct the 2nd OS interim analysis to test for efficacy at ~70% OS information fraction. If OS is significant at 70% IF, OS data will continue to be collected until all participants have died, are lost to follow up, or withdrawn consent, or for 2 years after the final OS analysis at 70% IF, whichever occurs first.
 

Study intervention
	
 
● Arm 1: Single agent Belantamab mafodotin. Belantamab mafodotin will be administered intravenously at 2.5 mg/kg on Day 1 (D1) of a Q3W schedule (e.g., 21-day cycle).
 
● Arm 2: Pomalidomide and low-dose dexamethasone (Pom/Dex). Pomalidomide will be administered orally at the approved starting dose of 4 mg daily on Days 1 to 21 of each 28-day cycle, with dexamethasone administered orally at a dose of 40 mg once weekly (Days 1, 8, 15, and 22). For participants over 75 years old, dexamethasone should be administered at the lower dose of 20 mg once weekly (Days 1, 8, 15, and 22).
 


Study intervention Assignment
	
 
● Approximately 320 participants will be randomized in a 2:1 ratio, in favor of Arm 1. Arm 1 (single agent belantamab mafodotin) will enroll approximately 214 participants and Arm 2 (pom/dex) will enroll approximately 106 participants. Participants will be stratified based on the following: previous treatment with anti-CD38 (Y/N), with a 40% global enrolment cap for participants with prior anti-CD38 treatment, stage (International Staging System [ISS]) (I/II or III), and number of prior lines of therapy (<math>\leq 3</math> vs <math>> 3</math>), with a 55%
 

Overview of Study Design and Key Features			
	global enrolment cap for participants with $\leq 3$ prior lines. No cross-over will be allowed until final OS analysis.		
Analysis	Analyses Timing from Randomization	Planned PFS analyses	Planned OS analyses
	~25 months	PFS final Approximately 151 PFS events and the first 320 randomized subjects have been followed for a minimum of 4 months c	OS IA for efficacy a ~100 OS events ~40% OS info
	48 months	N/A	OS IA for efficacy b ~175 OS events ~70% OS info
	>60 months	N/A	OS final b ~250 OS events
	a. Provided that final PFS analysis is significant. b. If PFS is significant and null hypothesis is not rejected at the 2 nd OS IA for efficacy. c. First dose of 320 th subject happens around 21 months		

## 2. STATISTICAL HYPOTHESES

### Primary endpoint PFS

The primary efficacy analysis will be the comparison of the distribution of PFS between the two treatment groups. Assuming proportional hazards for PFS, the following statistical hypothesis will be tested to address the primary efficacy objective at one-sided alpha level of 2.5%:

$$H_{01}: \theta_1 \geq 1 \text{ VS. } H_{A1}: \theta_1 < 1$$

where,  $\theta_1$  is the PFS HR (belantamab mafodotin arm vs. pom/dex arm).

### Key secondary endpoint OS

Assuming proportional hazards for OS, the following statistical hypotheses will be tested at one-sided alpha level of 2.5% if PFS is statistically significant:

$$H_{02}: \theta_2 \geq 1 \text{ VS. } H_{A2}: \theta_2 < 1$$

where,  $\theta_2$  is the OS HR (belantamab mafodotin arm vs. pom/dex arm).

[figure not shown]
### 2.1. Multiplicity Adjustment

The family-wise type I error for this study is strongly controlled at 2.5% (one-sided). A hierarchical testing procedure is adopted and the hypothesis testing of key secondary endpoint OS will only be performed if the primary endpoint PFS is statistically significant at PFS final analysis [Bretz, 2009; Li, 2017].

The hypothesis testing for key secondary endpoint OS will be conducted provided that the primary endpoint PFS is statistically significant at PFS final analysis. The type I error for OS is strongly controlled at 2.5% (one-sided) by a group sequential design with a Lan-DeMets (O'Brien-Fleming) alpha spending function [Lan, 1983] using information fractions of (0.4, 0.7, 1) with total one-sided type I error of 2.5%. More details about the hypothesis testing and overall alpha control are provided in Section 4.7.

### 3. ANALYSIS SETS

Analysis Set	Definition / Criteria	Analyses Evaluated
All Screened	
 
The All Screened Population will consist of all participants who sign the ICF to participate in the clinical trial. Participants in this population will be used for screen failure summary.
 
	
 
Study Population
 

Enrolled	
 
All participants who entered the study.
 
Note screening failures (who never passed screening even if rescreened) and participants screened but never enrolled into the study (Reserve, Not Used) are excluded from the Enrolled analysis set as they did not enter the study.
 
	
 
Study Population
 

Intent-to-Treat (ITT)	
 
ITT Population will consist of all randomized participants whether or not randomized treatment was administered. This population will be based on the treatment and strata to which the participant was randomized and will be the primary population for the analysis of efficacy data. Any participant who receives a treatment randomization number will be considered to have been randomized.
 
	
 
Study Population
 
Efficacy
 

mITT (modified ITT)	
 
All participants who have received at least 2 lines of prior therapies; randomized and received at least one dose of study treatment (participant randomized to the belantamab mafodotin arm but received pom/dex will be excluded and vice versa); with measurable disease at baseline.
 
	
 
Efficacy
 

Safety	
 
All randomized participants who take at least 1 dose of study intervention (any drug component). Participants will be analyzed according to the intervention they actually received.
 
	
 
Safety
 

Pharmacokinetic (PK)	
 
All participants in the Safety analysis set who had at least 1 non-missing PK assessment (Non-quantifiable [NQ] values will be considered as non-missing values).
 
Data should be reported according to the actual treatment
 
	
 
PK
 

1. measurable disease at baseline is defined as: a patient has at least one of the following measurements: a. Serum M-protein  $\geq 0.5$  g/dL ( $\geq 5$  g/L) or b. Urine M-protein  $\geq 200$  mg/24h or c. Serum FLC assay: Involved FLC level  $\geq 10$  mg/dL ( $\geq 100$  mg/L) and an abnormal serum free light chain ratio ( $<0.26$  or  $>1.65$ )

## **4. STATISTICAL ANALYSES**

### **4.1. General Considerations**

#### **4.1.1. General Methodology**

The Intent-to-Treat (ITT) analysis set will be used for all study population analyses and efficacy analyses, unless otherwise specified and Safety analysis set will be used for all safety analyses.

The stratified log-rank test and stratified Cox proportional hazards models will include the randomization stratification factors as “strata”. Unless otherwise specified, the stratification factors entered for randomization will be used in the primary analysis. If there is any mis-stratification, a supplementary analysis will be performed using the stratification data based on the clinical database.

Confidence intervals will use 95% confidence levels unless otherwise specified.

Unless otherwise specified, continuous data will be summarized using descriptive statistics: n, mean, standard deviation (std), median, minimum and maximum. Categorical data will be summarized as the number and percentage of participants in each category.

For efficacy analyses, only central lab values will be used.

#### **4.1.2. Baseline Definition**

For all endpoints, unless otherwise specified, the baseline value will be the latest pre-dose assessment with a non-missing value, including those from unscheduled visits. If time is not collected, Day 1 assessments are assumed to be taken prior to first dose and used as baseline. For participants who did not receive study treatment during the study, baseline will be defined as the latest, non-missing collected value.

For laboratory data, baseline will be the latest non-missing pre-dose value from central lab. If no central lab value is available, the latest non-missing pre-dose value from local lab will be used. For efficacy lab tests, only central lab values will be used.

For ECG analyses, if the latest, non-missing pre-dose values is from triplicate, the subject level baseline is defined as the mean of triplicate baseline assessments.

Unless otherwise stated, if baseline data is missing no derivation will be performed and baseline will be set to missing.

## 4.2. Primary Endpoint Analyses

### 4.2.1. Definition of endpoint

#### Progression-Free-Survival (PFS)

PFS is the primary endpoint of this study; it is defined as the time from randomization until the earliest date of PD, or death due to any cause. The analyses of PFS will be based on the ITT Analysis Set, unless otherwise specified.

### 4.2.2. Planned analysis of PFS

#### Overview of the planned analyses

- Primary analysis of PFS will be based on investigator-assessed response (per IMWG Kumar, 2016)
- Handling of intercurrent events for primary estimand (Table 1) are specified as the primary event and censoring rules in Table 2; Handling of intercurrent events for supplementary estimands 1&2 (Table 1) are specified as the alternative event and censoring rules 1&2 in Table 2, respectively;

The following sets of analyses will be conducted:

- [1]. Primary analysis of primary estimand ( investigator-assessed response + primary censoring rules);
- [2]. Primary analysis of supplementary estimand 1 ( investigator-assessed response + alternative censoring rules 1);
- [3]. Primary analysis of supplementary estimand 2 ( investigator-assessed response + alternative censoring rules 2);

**Table 2 Assignments for Primary and Alternative Progression and Censoring Dates for PFS Analysis**

Situation	Date of Event (Progression/Death) or Censoring	Outcome Event (Progression/Death) Or Censored
No (or inadequate) baseline tumor assessments  and the subject has not died (if the subject has died follow the rules for death indicated at the bottom of the table)	Randomization	Censored
No post-baseline assessments and the subject has not died (if the subject has died follow the rules for death indicated at the bottom of the table)	Randomization	Censored
Progression documented at scheduled visits and Progression documented without extended loss-to-follow-up time 	Date of assessment of progression	Event
Progression documented between scheduled visits and Progression documented without extended loss-to-follow-up time 	Date of assessment of progression	Event
	Date of next scheduled response assessment [SA1]	Event [SA1]
No progression (or death)	Date of last 'adequate' assessment of response 	Censored
New anticancer treatment started (prior to documented disease progression or death)  .	Date of last 'adequate' assessment of response  (on or prior to starting anti-cancer therapy)	Censored
	Date of starting new anticancer therapy [SA2]	Event [SA2]
Death without extended loss-to-follow-up time 	Date of death	Event
Death or progression after an extended loss-to-follow-up time 	Date of last 'adequate' assessment of response  prior to PD/death (prior to missed assessments)	Censored
	Date of death or progression [SA2]	Event [SA2]
Death or progression after an extended loss-to-follow-up time  from randomization	Date of randomization	Censored
Treatment discontinuation due to clinical PD before PD or death [SA2]	Date of treatment discontinuation [SA2]	Event [SA2]

[SA1]. Alternative rule 1 for handling of intercurrent events for supplementary estimand of PFS

[SA2]. Alternative rule 2 for handling of intercurrent events for supplementary estimand of PFS

[1]. Adequate baseline assessment is defined as at baseline, a patient has at least one of the following measurements: a. Serum M-protein  $\geq 0.5$  g/dL ( $\geq 5$  g/L) or b. Urine M-protein  $\geq 200$  mg/24h or c. Serum FLC assay: Involved FLC level  $\geq 10$  mg/dL ( $\geq 100$  mg/L) and an abnormal serum free light chain ratio ( $< 0.26$  or  $> 1.65$ )

[2]. An adequate assessment is defined as an assessment where the response is sCR, CR, VGPR, PR, MR, or SD.

[3]. If PD or death and New anti-cancer therapy occur on the same day assume the progression or death was documented first (e.g., outcome is progression or death and the date is the date of the assessment of progression or death). If anti-cancer therapy is started prior to any adequate assessments, censoring date should be the date of randomization.

- [4]. Extended loss-to-follow-up time = 6 weeks + 7 day window = 49 day window; Without extended loss-to-follow-up time is defined as:  $\leq 49$  days; after an extended loss-to-follow-up time is defined as:  $>49$  days. More details about extended loss-to-follow-up time are provided in Section 6.2.9.

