1.1.2. Estimands

Table 1 Estimands

Objective	Estimand Category	Estimand			Population Level Summary Measure
		Variable/Endpoint	Analysis Set	Intercurrent Event Strategy	
Primary Objective: To demonstrate the superiority of belantamab mafodotin compared to pomalidomide plus low dose dexamethasone (pom/dex) in PFS in participants with relapsed/refractory multiple myeloma (RRMM) [1]	Primary	PFS	ITT	
 
• Disease assessments between scheduled visits: treatment policy
 
• New anti-cancer therapy: while on treatment
 
• Extended loss to follow-up: while on treatment
 
• Treatment discontinuation: treatment policy
 
• Death: composite
 
	Hazard ratio for belantamab mafodotin vs pom/dex
	Supplementary 1	PFS	ITT	
 
• Disease assessments between scheduled visits: hypothetical
 
• New anti-cancer therapy: while on treatment
 
• Extended loss to follow-up: while on treatment
 
• Treatment discontinuation: treatment policy
 
• Death: composite
 
	Hazard ratio for belantamab mafodotin vs pom/dex
	Supplementary 2	PFS	ITT	
 
• Disease assessments between scheduled visits: treatment policy
 
• New anti-cancer therapy: composite
 
• Extended loss to follow-up: treatment policy
 
• Treatment discontinuation: composite
 
• Death: composite
 
	Hazard ratio for belantamab mafodotin vs pom/dex
Key Secondary Objective: To demonstrate the superiority of belantamab mafodotin compared to pomalidomide plus low dose dexamethasone (pom/dex) in OS in participants with relapsed/refractory multiple myeloma (RRMM) [1]	Primary	OS	ITT	Survival benefit regardless of subsequent anticancer therapies or treatment compliance 
 
• New anti-cancer therapy: treatment policy
 
• Treatment discontinuation: treatment policy
 
	Hazard ratio for belantamab mafodotin vs pom/dex

Objective	Estimand Category	Estimand			Population Level Summary Measure
		Variable/Endpoint	Analysis Set	Intercurrent Event Strategy	

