### 6.2.9. Extended Loss to Follow-up or Extended Time without an Adequate Assessment

For participants, if two or more scheduled disease assessments are missed and are then followed by an assessment of PD or death, PFS will be censored at the last adequate assessment prior to PD or death. When the scheduled disease assessment is every 3 weeks, a window of 49 days (6 weeks + 7 day window) will be used to determine whether there was an extended time without adequate assessment. That is, if the time difference between PD/death and last adequate assessment is more than 49 days, then PFS will be censored at the last adequate assessment prior to PD/death. In case there is no adequate assessment between PD/death and randomization date, and the time difference between PD/death and randomization date is more than 49 days, then PFS will be censored at the randomization date.

CCI

CCI

CCI

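### Table 2 has no alternative-rule-2 event line for progression or death after a gap counted from randomization, so supplementary PFS estimand 2 censors at day 0 some events that Table 1 says should count

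*SAP*

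**What the plan says.** Section 1.1.2, Table 1, lists for supplementary estimand 2: "Extended loss to follow-up: treatment policy". The primary estimand and supplementary estimand 1 use a while-on-treatment strategy for the same event. Supplementary estimand 2 also treats new anticancer therapy and treatment discontinuation as composite events.

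Section 4.2.2 makes Table 2 the implementation: "Handling of intercurrent events for supplementary estimands 1&2 (Table 1) are specified as the alternative event and censoring rules 1&2 in Table 2, respectively". The [SA2] tag is explained under that table as "Alternative rule 2 for handling of intercurrent events for supplementary estimand of PFS".

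Table 2 has two adjacent rows for progression or death after an extended gap:

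- **Gap after an adequate assessment.** The default is censoring at the last adequate assessment before the missed ones. An [SA2] line replaces this with an event on the date of death or progression.
- **Gap from randomization**, worded "Death or progression after an extended loss-to-follow-up time [4] from randomization". The only outcome is the date of randomization, censored. There is no [SA2] line.

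Note [4] sets the threshold: "Extended loss-to-follow-up time = 6 weeks + 7 day window = 49 day window", exceeded when the interval is more than 49 days. Note [2] reads: "An adequate assessment is defined as an assessment where the response is sCR, CR, VGPR, PR, MR, or SD". A progression or a non-evaluable result is therefore not an adequate assessment. For a participant with no adequate assessment and an interval above 49 days, Section 6.2.9 concludes: "then PFS will be censored at the randomization date".

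**The concern.** Under treatment policy, a missed-assessment gap does not change whether a later progression or death counts. Table 2 follows this for a participant with at least one adequate assessment and, on its face, not for a participant with none. Wherever alternative rule 2 departs from the default, Table 2 marks it with an [SA2] entry, so a programmer would apply the default to an unmarked row.

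An affected participant contributes neither an event nor time at risk. If such participants are unevenly spread between the arms, the supplementary hazard ratio moves, and the estimate differs from the estimand defined in Table 1.

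**Working it through.** **1. The plan's own design figures, for scale.** Section 5.2 gives 151 PFS events, HR 0.57, 90% power, one-sided 0.025, 2:1 allocation and a critical HR of 0.713.

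- Events (Schoenfeld) = (1.960 + 1.282)² / [(2/3)(1/3)(ln 0.57)²] = 10.51 / (0.2222 × 0.3160) ≈ 150. With 151 events the power is 90.3%.
- SE of the log HR = 1/√(151 × 2/9) = 0.173. Critical HR = exp(−1.96 × 0.173) = 0.713.

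The stated figures reproduce. The point does not depend on them.

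**2. Two participants under alternative rule 2.** Neither starts new therapy or stops for clinical progression, and both die on day 60.

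| | Adequate assessment | Interval to death | Table 2 row | Outcome under [SA2] |
|---|---|---|---|---|
| A | SD on day 10 | 60 − 10 = 50 days, > 49 | Gap after an adequate assessment | Event, day 60 |
| B | None | 60 days from randomization, > 49 | Gap from randomization | Censored, day 0 |

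Table 1 calls for an event on day 60 in both cases. Because progression is not an adequate assessment, a participant whose first evaluable result is a progression after day 49 falls in the same row as B.

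**3. Who is affected.** Among participants with no adequate assessment, Table 2 already gives an event under alternative rule 2 for:

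- death or progression within 49 days of randomization;
- start of new anticancer therapy before progression or death;
- treatment discontinuation due to clinical progression.

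The loss is confined to progression or death after day 49 with none of these earlier events.

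**4. Upper bound on the number.** The SAP gives no count of participants without an adequate assessment, so the share is an assumption. With the exponential medians in Section 5.2 and 49 days = 1.61 months:

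- P(time > 49 days), pom/dex: 0.5^(1.61/4) = 0.757.
- P(time > 49 days), belantamab mafodotin: 0.5^(1.61/7) = 0.853.
- Weighted 2:1: (2/3)(0.853) + (1/3)(0.757) = 0.821.

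Lost events ≤ 320 × share × 0.821: about 3, 5, 13 and 26 for shares of 1%, 2%, 5% and 10%. These bounds assume that every such event is eventually observed and that no other [SA2] line catches it.

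**5. Possible shift in the hazard ratio.** Simulated trials used 106 vs 214 participants, exponential medians of 4 and 7 months, 20 months of uniform accrual and a cut-off at month 25. An unstratified Cox model was fitted before and after removing early events (days 50 to 150).

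| Events removed, pom/dex vs belantamab mafodotin | HR, 150 trials | HR, repeat with 300 trials |
|---|---|---|
| 5 vs 2 | 0.584 → 0.594 | 0.566 → 0.575 |
| 10 vs 4 | 0.564 → 0.583 | 0.573 → 0.593 |
| 10 vs 0 | 0.568 → 0.600 | 0.576 → 0.609 |
| 3 vs 3 | 0.560 → 0.560 | essentially unchanged |

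The largest shift is ln(0.600/0.568) = 0.055 on the log scale (0.056 in the repeat), against a standard error of 0.173 at 151 events.

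The numbers removed are assumed. The set-up also implies more events than the plan: with follow-up uniform on 5 to 25 months, expected events are 214 × 0.735 + 106 × 0.882 ≈ 251, not 151. The starting HRs differ between scenarios (0.560 to 0.584) through simulation noise. Only the order of magnitude is informative.

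**The case against.** The best defence is that the intent is plain. Table 1 says treatment policy, Section 4.2.2 says Table 2 implements it, and the first gap row is worded generally enough to cover any gap. On this reading the from-randomization row only supplies a censoring date where no adequate assessment exists. Table 4 uses the same pair of rows for TTP, which has no alternative rule, and under alternative rule 2 no censoring date is needed.

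This stands as evidence of intent. It does not settle how Table 2 executes, because the first row's default date presupposes an earlier adequate assessment and the more specific row was written for participants who have none. Following the specific row contradicts Table 1.

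Some stronger readings are tempting but unsupported:

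- **That the analysis drops everyone without an adequate assessment.** It does not. Early events, new therapy and discontinuation for clinical progression remain events.
- **That Section 6.2.9 independently confirms the censoring.** Its earlier sentences also censor after a gap without exception, and Table 2 expressly overrides those for alternative rule 2. The section states default rules only, so its silence on [SA2] proves nothing.
- **That new-therapy starters without a post-baseline assessment are wrongly censored.** The no-baseline and no-post-baseline rows and the last sentence of note [3] do point to censoring at randomization, and Table 2 has no precedence rule. But the new-therapy row has its own [SA2] event line and Table 1 says composite, so the intent is clear. This needs clarification only.
- **That supplementary estimand 2 is the designated check on missed assessments and early switching.** Section 4.2.5.1 gives its method and states no such purpose.

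**Conclusion.** The point holds as a contradiction within the SAP. Table 1 requires an event; the from-randomization row of Table 2, applied as written, censors it at day 0. It reaches only progression or death more than 49 days after randomization with no adequate assessment and no earlier [SA2] event.

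A reader might infer that the primary PFS result or the type I error is at risk. It is not. The primary estimand and supplementary estimand 1 use a while-on-treatment strategy for this event, so the row does not conflict with them. Section 4.2.3 reserves the stratified log-rank test for the primary estimand, and supplementary estimand 2 has only Kaplan-Meier and Cox estimates, in ITT (Section 4.2.5.1) and mITT (Section 4.2.5.2).

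The size is unknown because the number of such participants is not in the document. Under the assumed numbers above, the hazard ratio moved by about 0.01 to 0.03, and not at all when losses were equal. The direction depends on which arm loses more events. The correction is worth making because the rule is wrong as written and the repair is short, not because a large bias is expected.

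**What to change.** - In Table 2, add an [SA2] line to the from-randomization gap row: date of death or progression, Event.
- In Section 6.2.9, state that all the PFS censoring rules there, not only the last sentence, apply to the primary rule and alternative rule 1 only.
- As a clarification in the same edit, state that under alternative rule 2 the new-anticancer-therapy event line takes precedence over the no-baseline and no-post-baseline censoring rows and over the last sentence of note [3].

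The cost is a few lines of SAP text and a small change to the derivation program for supplementary estimand 2. No new data are needed, and no confirmatory analysis changes.

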#### **4.2.5. Supplementary Analyses**

##### **4.2.5.1. Analysis of Supplementary Estimand of PFS**

Additional analyses of the supplementary estimands 1&2 (i.e. handling of intercurrent events based on alternative event and censoring rules 1&2) of PFS will be conducted based on investigator-assessed response.

These additional analyses will only use the Kaplan-Meier estimates and Cox proportional hazards model stratified by randomization factors described in Section [4.2.3](#).

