1. Subsequent disease assessment is defined as the next adequate (not missing or NE) disease assessment following the first timepoint before (or on the same date of) start of new anti-cancer therapy except for confirmation of PD, for which PD or death due to PD after new anti-cancer therapy are considered for confirmation of PD. No minimal time interval is required for the subsequent disease assessment, but a different sample is required for confirmation.
2. SD does not need to be confirmed.
3. PD due to imaging (i.e., plasmacytoma or bone lesion) does not need to be confirmed.
4. Where criteria are not mutually exclusive, take the first that applies.

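### PFS supplementary estimand 2: Table 2 gives both an event and a censoring outcome to a living participant with no post-baseline assessment who starts new therapy or stops for clinical progression

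*SAP*

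**What the plan says.** Table 1 (SAP Section 1.1.2) defines supplementary estimand 2 for PFS with "New anti-cancer therapy: composite", and treats treatment discontinuation as composite too. Section 4.2.2 makes Table 2 the operative rule: the intercurrent-event strategies of supplementary estimands 1 and 2 "are specified as the alternative event and censoring rules 1&2 in Table 2, respectively".

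Three parts of Table 2 bear on the point:

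- **New-therapy row.** The primary line censors at the last adequate assessment, "on or prior to starting anti-cancer therapy". The [SA2] line records an event, dated "Date of starting new anticancer therapy". It does not require that an assessment came first.
- **Clinical-PD row.** This exists only under [SA2]: stopping treatment for clinical progression is an event on the discontinuation date, again with no prior assessment required.
- **No-assessment row.** For "No post-baseline assessments and the subject has not died" the date is randomization and the outcome is censored. Death is the only exception, and there is no [SA2] line.

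Footnote [3], attached to the new-therapy row, ends: "If anti-cancer therapy is started prior to any adequate assessments, censoring date should be the date of randomization". Section 4.2.5.1 limits the use of the result: "These additional analyses will only use the Kaplan-Meier estimates and Cox proportional hazards model stratified by randomization factors".

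**The concern.** Supplementary estimand 2 counts leaving for other therapy as failure, where the primary estimand censors it. The trial is open-label, and the ITT set keeps participants who were randomized but never treated. Someone who declines the assigned arm and goes straight to another therapy is therefore the kind of case this estimand is there to count.

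If that person has no post-baseline assessment, Table 2 also places them in a row that censors at randomization. Coding that row as written removes the event that the estimand's definition calls for. Such losses need not be balanced between arms.

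**Working it through.** **1. The rows side by side, under alternative rule 2.** Take a living participant with no post-baseline assessment.

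| What happens | [SA2] line | No-assessment row |
|---|---|---|
| Starts new anti-cancer therapy | Event, date therapy starts | Censored, randomization |
| Stops treatment for clinical PD | Event, date of discontinuation | Censored, randomization |
| Dies | Not applicable | Sent to the death rows |

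The exception for death shows that the table recognizes an overlap and resolves it in one case. The other two overlaps are unresolved, and no general order of precedence is stated.

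**2. Who is affected.** Only living participants who never have a post-baseline assessment. Someone assessed later, or who dies, is outside the row. SAP Section 1.2 says that, after discontinuation for reasons other than PD, disease evaluations stop when new anti-cancer treatment starts. A participant who switches before the first assessment would therefore usually stay in the row.

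**3. The plan's own figures.** None is stated for supplementary estimand 2. The primary design figures reproduce. With HR 0.57, one-sided alpha 0.025, 90% power and 2:1 allocation, the Schoenfeld formula gives (1.960 + 1.282)² / [(2/9) × (ln 0.57)²] ≈ 150 events against 151 stated. At 151 events, power is 90.3% and the critical hazard ratio is exp(−1.960/√(151 × 2/9)) = 0.713. None of these depends on the overlap.

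**4. Effect on the supplementary hazard ratio.** A record censored at randomization is in no later risk set, so it adds nothing to the Cox likelihood or the Kaplan-Meier curve. The number affected is an assumption: 3 to 15 of 320, that is 3/320 = 0.9% to 15/320 = 4.7%.

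Simulation inputs from the SAP are 214 and 106 participants, median PFS of 7 and 4 months, exponential times and uniform accrual over 20 months, with the cut-off at month 25. The affected participants are either events within about the first month or censored at randomization. The model is an unstratified Cox model, with 2,000 to 3,000 simulated trials per split.

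| Affected, belantamab / pom-dex | HR if censored minus HR if event |
|---|---|
| 2 / 1 | 0.575 − 0.579 = −0.004 |
| 4 / 2 | 0.575 − 0.583 = −0.008 |
| 6 / 3 | 0.577 − 0.588 = −0.011 |
| 6 / 0 | 0.575 − 0.602 = −0.027 |
| 0 / 3 | +0.015 |
| 2 / 5 | +0.016 |
| 4 / 11 | +0.038 |

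Censoring lowers the hazard ratio when departures follow the 2:1 allocation or concentrate on belantamab. It raises it when they concentrate on pom/dex. The last split is extreme: 11 of 106 is about 10% of the control arm.

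**5. Scale.** The standard deviation of the log hazard ratio across simulated trials is about 0.135. The largest shift is about 0.038/0.57 = 0.067 on the log scale, or half of that; most are far smaller. Under these exponential assumptions the simulated data hold about 250 events at month 25. With 151 events, a given number of lost events would weigh more (15/250 = 6% against 15/151 = 10%).

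**The case against.** The strongest reply is that Table 2 only works if the specific situation overrides the general one. Its row for no progression or death stands above the new-therapy row and would otherwise absorb every non-progressing participant who switched. Read that way, the [SA2] lines govern and no event is lost. This is a sensible reading and it agrees with Table 1. But the table does not state it, and the no-assessment row lists its exceptions and names only death. A programmer who follows that row is following the text.

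Three stronger readings are tempting, and the SAP does not support them:

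- *Footnote [3] itself removes the events.* It fixes a censoring date. Only the primary line censors, and only that line needs a fallback when no adequate assessment exists. An [SA2] event has no censoring date to set. The footnote is merely not expressly limited to the lines that censor.
- *Anyone who starts therapy before a first assessment is lost.* Participants who are assessed later, or who die, do not fall in the row.
- *Censoring wins because the SAP takes the first matching row.* The note "Where criteria are not mutually exclusive, take the first that applies" belongs to Table 3, on response confirmation. The row order just described shows that it cannot be Table 2's convention.

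SAP Section 1 leaves further data-handling detail to the Output and Programming Specification, which might settle the coding. It would then have to depart from one of two rules that the SAP states.

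**Conclusion.** The conflict is real but narrow. Under alternative rule 2, two stated rules give opposite outcomes for a living participant with no post-baseline assessment who starts new therapy or stops for clinical progression. Loss of these events is one possible coding, not something the table clearly prescribes.

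The size rests on assumed counts, because the SAP gives none, and on an exponential model. Within those assumptions the supplementary hazard ratio moves by roughly 0.004 to 0.04. A reader might infer a bias against or in favour of belantamab mafodotin; neither can be claimed, because the sign depends on the arm split.

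The stratified log-rank test is confined to the primary estimand (Section 4.2.3), so the primary result, alpha, power and the 151-event target are untouched. This is a desirable clarification, not a condition for the trial's validity.

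**What to change.** Add an [SA2] line to the no-assessment row of Table 2: if new anti-cancer therapy was started, or treatment was stopped for clinical PD, the outcome is an event on the earlier of those dates. Alternatively, state under Table 2 that [SA2] event lines take precedence over the censoring rows when alternative rule 2 is applied.

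As a clarification only, limit the last sentence of footnote [3] to the primary rule and alternative rule 1.

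The cost is two lines of SAP wording and the matching program specification. No new data are needed and the primary analysis does not change.
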